#### *4.3.8.1.1 Pre-treatment Adverse Events Analysis*

The following type of events will be summarized by SOC and PT:

- 1) Adverse Events
- 2) Serious Adverse Events (SAE)
- 3) Grade 3-5 AE (CTCAE; version 5.0)
- 4) Grade 5 AE (CTCAE; version 5.0)

Pre-treatment AEs for subjects who are screen failure will be listed.

#### *4.3.8.1.2 Treatment Emergent Adverse Events Analysis*

The following type of events will be summarized by SOC and PT:

- 1) Adverse Events
- 2) Serious Adverse Events (SAE)
- 3) Grade 3-5 AE

- 4) Grade 5 AE
- 5) AE leading to treatment discontinuation
- 6) AE leading to study discontinuation
- 7) AE leading to dose reduction
- 8) AE leading to dose interruption
- 9) Related AE
- 10) Related Grade 3-5 AE
- 11) Related Grade 5 AE

#### *4.3.8.1.3 Post-treatment Adverse Events Analysis*

The following type of events will be summarized by SOC and PT:

- 1) Adverse Events
- 2) Serious Adverse Events (SAE)
- 3) Grade 3-5 AE
- 4) Grade 5 AE
- 5) AE leading to study discontinuation
- 6) Related AE
- 7) Related Grade 3-5 AE
- 8) Related Grade 5 AE

#### *4.3.8.2 Adverse events of Special Interest*

The overall frequency and incidence of subjects with treatment-emergent Adverse Events of special interest (AESI) (as collected in AE eCRF form) will be tabulated by PTs which were considered AESI overall and by apraglutide dose levels and overall:

- Injection site reactions
- Gastrointestinal obstructions
- Gallbladder, biliary and pancreatic disease
- Fluid overload
- Colorectal polyps
- Newly Diagnosed malignancies

- Systemic hypersensitivity

The following type of AESIs will be summarized by SOC and PT:

- 1) Adverse Events
- 2) Serious Adverse Events (SAE)
- 3) Grade 3-5 AE (CTCAE; version 5.0)
- 4) Grade 5 AE (CTCAE; version 5.0)
- 5) AE leading to study discontinuation
- 6) Related AE
- 7) Related Grade 3-5 AE (CTCAE; version 5.0)
- 8) Related Grade 5 AE (CTCAE; version 5.0)

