Unless specified otherwise, endpoints described in this document will be analyzed at both analysis steps: Primary Analysis and EOT Analysis.

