##### 4.3.8.1 *Adverse events*

Adverse events (AEs) will be coded using Medical Dictionary for Regulatory Activities (MedDRA) version 24.0. The severity of all adverse events will be graded according to the National Cancer Institute (NCI) Common Terminology Criteria for Adverse Event (CTCAE) [NCI-CTCAE, 2017], version 5 (publication date: 27 November 2017). Adverse Events will be summarized descriptively by the frequency and incidence of subjects experiencing events corresponding to System Organ Class (SOC) MedDRA and Preferred Term (PT). Subjects with multiple occurrences of events will only be counted once at the maximum severity/grade to trial therapy for each PT, SOC, and overall. Summaries will be ordered by decreasing overall incidence in SOC; and by decreasing overall incidence of PTs within a SOC .

The overall observation period will be divided into mutually exclusive categories, including pre-treatment, on-treatment (treatment emergent), post-treatment:

- A treatment-emergent adverse event (TEAE) is defined as an adverse event with a start date and time on or after the first administration of apaglutide or having been present prior to the first dose of apaglutide but worsening in severity after starting treatment relative to the pre-treatment state. Adverse events are considered as TEAE until 28 days after the last dose of apaglutide received.
- A pre-treatment Adverse Event is defined as an AE occurring after the signature of the ICF and before the first dose.
- A post-treatment adverse event is defined as an AE occurring 28 days after the last dose.

Adverse events that are reported as possibly, probably, or definitely related to apaglutide therapy will be counted as related to trial therapy. Adverse events with a missing relationship will be considered as "related".

An overview of all Adverse Events will be provided.

All SAEs or AEs that led to withdrawal will be listed, Serious Adverse Events (SAEs) will be flagged within the listing.

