#### 4.3.8.3 Adverse events of Particular Interest

Treatment-emergent adverse events of particular interest (AEPI) are Sponsor defined and will be derived programmatically based on Sponsor-defined list of preferred terms (see Table 4-2), according to the Safety Signal Detection Plan (V1.0).

**Table 4-2: Sponsor-defined Adverse Events of Particular Interest. SMQ = Standardised MedDRA Queries, HLT= High Level Term.**

AEPI	Definition
Acceleration of neoplastic growth including Intestinal neoplastic growth/hypertrophic effect including polyps	SOC: Neoplasms benign, malignant and unspecified (including cysts and polyps)
Benign neoplasia of the Gastrointestinal tract including the hepatobiliary system (not including polyps).	SMQ: Gastrointestinal premalignant disorders (Level 1, narrow terms) SMQ: Biliary neoplasms benign (incl cysts and polyps) (Level 3, narrow terms)
Gastrointestinal obstruction	SMQ: Gastrointestinal obstruction (Level 2, narrow terms)
Gastrointestinal stoma obstruction	PT: Intestinal anastomosis complication, Stoma Obstruction

Increase of the liver transaminases	SMQ Drug related hepatic disorders - comprehensive search (broad and narrow terms)
Embryofetal toxicity	SMQ: Pregnancy and neonatal topics (broad and narrow terms)
Biliary adverse events	SMQ: Functional, inflammatory and gallstone related biliary disorders (broad and narrow terms)
Pancreatic adverse events	HLT: Acute and chronic pancreatitis HLT: pancreatitis disorders necrotizing entecorolitis (NEC)
Cardiovascular AEs associated with fluid overload	SMQ: Haemodynamic oedema, effusions and fluid overload (Narrow) SMQ. Cardiac failure (broad and narrow terms)
Cecal AE (additional from interim analysis)	LLT: Cecal diverticulitis, Cecal hemorrhage, Cecal infection, Cecal inflammation, Cecal lesion excision, Cecal obstruction, Cecum perforation, Cecal polyp, Cecal ulcer, Cecal volvulus, Cecum rupture

Treatment-emergent AEPIs will be summarized by SOC and PT and in total by apraglutide dose levels and in total for the following, where subjects with multiple adverse events will be counted only once per SOC or PT:

- 1) Treatment-emergent AEPIs
- 2) IMP-related TEAE
- 3) Grade 3-5 TEAE
- 4) Serious TEAEs
- 5) TEAEs leading to IMP dose reduction
- 6) TEAEs leading to IMP interruption
- 7) TEAEs leading to IMP permanently discontinued
- 8) AEs leading to death.

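### At the end-of-trial analysis, the opening AESI table closes 28 days after the last dose, so it leaves out polyps and new malignancies first dated at treatment completers' routine Week 52 and Week 104 examinations

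*SAP*

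**What the plan says.** **The window.** SAP 4.3.8.1 splits observation into non-overlapping pre-treatment, on-treatment and post-treatment periods. On the end of the on-treatment period it says: "Adverse events are considered as TEAE until 28 days after the last dose".

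**The AESI tables.** SAP 4.3.8.2 has two parts. In the first, "subjects with treatment-emergent Adverse Events of special interest (AESI) (as collected in AE eCRF form) will be tabulated by PTs", followed by the seven groupings, which include colorectal polyps and newly diagnosed malignancies. The second begins "The following type of AESIs will be summarized by SOC and PT" and lists eight types of event. It names no period.

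**Later events.** Section 4.3.8.1.3, "Post-treatment Adverse Events Analysis", tabulates them by SOC and PT, with no AESI grouping.

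**Timing of the analyses.** SAP section 1: "Unless specified otherwise, endpoints described in this document will be analyzed at both analysis steps: Primary Analysis and EOT Analysis". Nothing exempts the AESI tables, so the same window applies at EOT.

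**The protocol.** Section 1.5.2.1 lists AESI incidence as a safety endpoint. Section 7.6.2 plans individual and cumulative incidence of the AESI groupings by dose and does not confine this to treatment-emergent events. Section 7.6.1 names AESIs separately from TEAEs. Section 5.8.1 and SAP Table B2 place polyp imaging at Weeks 52 and 104. Table B2 also marks it at the early treatment discontinuation visit.

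**The concern.** Safety is the primary objective. Protocol 1.8.1 gives accelerated neoplastic growth and polyp growth as possible risks of the drug class, and 1.8.2 cites mid- and longer-term checks for new polyps as a safeguard. Polyps found at screening must be removed before randomization, so in a treatment completer the first routine chance to see a new one is the Week 52 examination.

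If the AESI table stops before that examination, its polyp row at EOT says little about what the follow-up found. A zero could mean only that no completer was routinely examined inside the window. Someone reading that table as the AESI incidence of the trial would take a structurally low count for the answer to a listed safety endpoint.

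**Working it through.** **Inputs**

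- Treatment-emergent window: last dose + 28 days (SAP 4.3.8.1).
- Possible last doses of a completed course: Week 7, Week 12 or, with optional or flare treatment, up to Week 25 (SAP 2.1). Dosing visits have a window of ±1 day.
- Week 52 visit: Day 364 ± 2 weeks. Week 104 visit: Day 728 ± 4 weeks (SAP Table B2).

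**Step 1: reproduce the plan's own limit.** Latest dose = 25 × 7 + 1 = Day 176, which matches footnote 3 to protocol Figure 3.

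**Step 2: latest window end** = 7 × week of last dose + 1 + 28.

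**Step 3: earliest routine examinations.** Week 52: 364 − 14 = Day 350. Week 104: 728 − 28 = Day 700.

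**Step 4: smallest gap** = earliest examination − latest window end.

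| Last dose | Latest window end | Gap to Week 52 examination | Gap to Week 104 examination |
|---|---|---|---|
| Week 7 | 49 + 1 + 28 = Day 78 | 350 − 78 = 272 days | 700 − 78 = 622 days |
| Week 12 | 84 + 1 + 28 = Day 113 | 350 − 113 = 237 days | 700 − 113 = 587 days |
| Week 25 | 175 + 1 + 28 = Day 204 | 350 − 204 = 146 days | 700 − 204 = 496 days |

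These are protocol days. SAP 4.1.1 has no Day 0, so its analysis days are one higher throughout and the gaps are unchanged.

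**Step 5: share of the nominal 728 days outside the window** (nominal dosing days): (728 − 77)/728 = 89%, (728 − 112)/728 = 85%, (728 − 203)/728 = 72%.

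**Step 6: is the narrowing declared?** SAP section 6 lists 12 changes from the protocol. Item 10 extends infections and sepsis to the end of the trial. No item concerns the AESI period.

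**Step 7: what the second AESI list might cover.** Its eight items are the same, in the same order, as the eight in the post-treatment list (4.3.8.1.3). It lacks three items of the eleven-item treatment-emergent list (4.3.8.1.2): treatment discontinuation, dose reduction and dose interruption. That fits a list not confined to the treatment-emergent period, but it does not show whether the list covers all periods or only the post-treatment one. It also follows directly on a treatment-emergent table.

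**The case against.** The strongest reply is that the information is reported elsewhere. Late events are collected to the EOT visit (protocol section 6) and tabulated by SOC and PT, with severity and relatedness, in 4.3.8.1.3. If the second AESI list covers all periods, it already counts each subject once per PT and SOC through EOT, under the counting rule of 4.3.8.1. The SAP also promises an overview of all adverse events, and the table specifications are in a separate document. All of this stands. A reader might infer that late polyps go unreported, or that no planned output can contain the full count; the documents support neither. What remains is that the one table tied explicitly to the groupings is treatment-emergent, and the list that could fill the gap does not state its period.

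Protocol 7.6.2 can also be read more narrowly. It sets no period at all, and cumulative may mean all groupings together. The stand-alone tables listed in 7.6.1 are TEAE tables. So 7.6.2 does not promise a first-dose-to-EOT count. It does plan AESI incidence without the limit that the SAP adds.

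A reader might carry the point over to the adverse events of particular interest in 4.3.8.3, which are also limited to treatment-emergent events: "Treatment-emergent adverse events of particular interest (AEPI) are Sponsor defined". The protocol has no such category, so that limit departs from nothing in it. The first row of Table 4-2 is a whole SOC ("SOC: Neoplasms benign, malignant and unspecified (including cysts and polyps") and can largely be read from the post-treatment SOC line. The second uses standardised queries such as "SMQ: Gastrointestinal premalignant disorders (Level 1, narrow terms", which SOC/PT tables do not show as a group, but by its own label it excludes polyps.

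Finally, treatment-emergent and post-treatment rows cannot strictly be added, since one subject may be in both. For polyps in completers the overlap should be small, because no routine examination falls inside the window. It should not be presented as a large uncertainty.

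**Conclusion.** The point holds for the opening AESI table at the EOT analysis. For subjects who complete treatment, neither of the two routine post-screening polyp examinations can fall inside the treatment-emergent window. The margin is at least 146 days at Week 52 and 496 days at Week 104. Polyps and new malignancies first dated at those examinations are excluded from that table by rule, and the SAP does not record this as a change from the protocol.

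This rests on onset being dated at the examination. Events with missing or inconclusive dates default to treatment-emergent (SAP 4.1.2), and off-schedule or clinical findings during treatment can fall inside the window. Early discontinuers are imaged 28 to 35 days after the last dose, at the edge of the window or beyond it.

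The number of events affected cannot be derived from the documents, so no percentage is given. Nor is a claim made about the Primary Analysis: how many subjects reach a Week 52 examination by the 01 Dec 2023 cut-off is not stated. The defect is one of presentation for a listed safety endpoint. It is worth correcting because the correction is cheap, not because a signal would be hidden.

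**What to change.** For the EOT analysis, add to SAP 4.3.8.2 the number and percentage of subjects with any colorectal polyp, and with any newly diagnosed malignancy, with onset from first dose to end of trial. Give these by dose level and in total, each subject counted once per grouping, with the treatment-emergent count as a sub-row. State that the second AESI list covers first dose to end of trial. Extending the neoplasia rows of Table 4-2 in the same way is optional.

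The cost is a few extra rows in the EOT tables and one sentence in 4.3.8.2. No new data, visits or procedures are needed.

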#### 4.3.8.3 Adverse events of Particular Interest

Treatment-emergent adverse events of particular interest (AEPI) are Sponsor defined and will be derived programmatically based on Sponsor-defined list of preferred terms (see Table 4-2), according to the Safety Signal Detection Plan (V1.0).

**Table 4-2: Sponsor-defined Adverse Events of Particular Interest. SMQ = Standardised MedDRA Queries, HLT= High Level Term.**

AEPI	Definition
Acceleration of neoplastic growth including Intestinal neoplastic growth/hypertrophic effect including polyps	SOC: Neoplasms benign, malignant and unspecified (including cysts and polyps)
Benign neoplasia of the Gastrointestinal tract including the hepatobiliary system (not including polyps).	SMQ: Gastrointestinal premalignant disorders (Level 1, narrow terms) SMQ: Biliary neoplasms benign (incl cysts and polyps) (Level 3, narrow terms)
Gastrointestinal obstruction	SMQ: Gastrointestinal obstruction (Level 2, narrow terms)
Gastrointestinal stoma obstruction	PT: Intestinal anastomosis complication, Stoma Obstruction

Increase of the liver transaminases	SMQ Drug related hepatic disorders - comprehensive search (broad and narrow terms)
Embryofetal toxicity	SMQ: Pregnancy and neonatal topics (broad and narrow terms)
Biliary adverse events	SMQ: Functional, inflammatory and gallstone related biliary disorders (broad and narrow terms)
Pancreatic adverse events	HLT: Acute and chronic pancreatitis HLT: pancreatitis disorders necrotizing entecorolitis (NEC)
Cardiovascular AEs associated with fluid overload	SMQ: Haemodynamic oedema, effusions and fluid overload (Narrow) SMQ. Cardiac failure (broad and narrow terms)
Cecal AE (additional from interim analysis)	LLT: Cecal diverticulitis, Cecal hemorrhage, Cecal infection, Cecal inflammation, Cecal lesion excision, Cecal obstruction, Cecum perforation, Cecal polyp, Cecal ulcer, Cecal volvulus, Cecum rupture

Treatment-emergent AEPIs will be summarized by SOC and PT and in total by apraglutide dose levels and in total for the following, where subjects with multiple adverse events will be counted only once per SOC or PT:

- 1) Treatment-emergent AEPIs
- 2) IMP-related TEAE
- 3) Grade 3-5 TEAE
- 4) Serious TEAEs
- 5) TEAEs leading to IMP dose reduction
- 6) TEAEs leading to IMP interruption
- 7) TEAEs leading to IMP permanently discontinued
- 8) AEs leading to death.

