## LIST OF ABBREVIATIONS

Abbreviation	Definition
ADA	Anti-Drug Antibodies
ADaM	Analysis Data Model
AE	Adverse Event
AEPI	Adverse Event of Particular Interest
AESI	Adverse Event of Special Interest
aGVHD	Acute Graft Versus Host Disease
alloSCT	Allogeneic Hematopoietic Stem Cell Transplantation
ALL	Acute Lymphoblastic Leukemia
ALP	Alkaline Phosphatase
ALT	Alanine Aminotransferase
AML	Acute Myelogenous Leukemia
ANLL	Acute Non-lymphocytic Leukemia
AST	Aspartate Aminotransferase
BAT	Best Available Therapy
BMI	Body Mass Index
BOR	Best Overall Response
cGVHD	Chronic Graft Versus Host Disease
CI	Confidence Interval
CM	Concomitant Medication
CML	Chronic Myelogenous Leukemia
CMV	Cytomegalovirus
CNI	Calcineurin Inhibitor
CR	Complete Response
CTCAE	Common Terminology Criteria for Adverse Event
CTR	Clinical Trial Report
DoR	Duration of Response
ECG	Electrocardiogram
eCRF	Electronic Case Report Form
EDC	Electronic Data Capture
EOT	End of Trial

Abbreviation	Definition
EQ-5D-5L	EuroQol-5 Dimension – 5 Level Survey
EQ VAS	EuroQol Visual Analog Scale
FA	Final Analysis
FACT-BMT	Functional Assessment of Cancer Therapy – Bone Marrow Transplantation
FAS	Full Analysis Set
FDA	Food and Drug Administration
GFR	Glomerular Filtration Rate
GGT	Gamma Glutamyl Transferase
GI	Gastrointestinal
HLT	High Level Term
HR	Hearth Rate
IA	Interim Analysis
ICE	Intercurrent Event
ICF	Informed Consent Form
ID	Subject Identifier
IMP	Investigational Medicinal Product
ISR	Injection Site Reaction
iSRC	Independent Safety Review Committee
IV	Intravenous
MAGIC	Mount Sinai Acute Graft Versus Host Disease International Consortium
MAP	MAGIC Algorithm Probability
MDS	Myelodysplastic Syndrome
MedDRA	Medical Dictionary for Regulatory Activities
MH	Medical History
MP	Methylprednisolone
MPN	Myeloproliferative Neoplasms
NCI	National Cancer Institute
NE	Not Evaluable
NEC	Necrotizing Entecorolitis
OR	Overall Response

Abbreviation	Definition
PA	Primary Analysis
PK	Pharmacokinetic
PNH	Paroxysmal Nocturnal Hemoglobinuria
PO	Per Os (oral administration)
POC	Proof of Concept
PR	Partial Response
PR	Procedure
PR	Pulse Rate
PT	Preferred Term
Q1	First Quartile
Q3	Third Quartile
QoL	Quality of Life
QTcF	Fridericia-corrected QT interval
REG3 $\alpha$	Regenerating Islet-Derived Protein 3 Alpha
RUX	Ruxolitinib
SAE	Serious Adverse Event
SAP	Statistical Analysis Plan
SAS	Safety Analysis Set
SD	Standard deviation
SDTM	Study Data Tabulation Model
SI	International System of Units
SMQ	Standardised MedDRA Queries

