#### *4.3.9.11 Incidence of malignancy relapse up to 2 years post-first dose of apaglutide*

The malignancy relapse/progression time is defined as the time from the date of the first dose to the date of hematologic malignancy relapse/progression.

Hematologic malignancy relapse/progression will be identified by manual review of reported malignancies or relapses in the AE data against the Underlying disease history CRF by the medical team, and confirmed with Sponsor. The list of identified hematologic malignancy relapse/progression will be finalized prior to the data base lock both for the Primary and the EOT analysis.

The malignancy/relapse progression will be summarized using Kaplan-Meier estimator. The number and percentage of subjects experiencing an event, and subjects censored will be summarized by apaglutide dose levels and in total. The median time-to-event will be presented where possible, along with the range and the associated two-sided 95% Brookmeyer-Crowley confidence interval. The event-free rate with 95% CI using Greenwood's formula will be provided for selected time points (e.g., 1, 3, 6, 12 and 24 months).

Plots of the Kaplan-Meier estimate for the malignancy/relapse progression will be presented by apaglutide dose levels and in total.

Subject for which no malignancy/relapse progression event occurs will be right censored at their last follow-up visit.

Incidence of malignancy/relapse progression will be analyzed only for the EOT analysis.

*4.3.9.12 Overall Survival up to 2 years post-first dose of apaglutide*

The overall survival time is defined as the time from the date of the first dose to the date of death due to any cause.

The last date known to be alive for each individual subject may be determined using, but not limited to, the following dates recorded on the eCRF:

- AE start and stop dates
- Study treatment start and stop dates
- Sample collection date for laboratory assessments
- Dates of any performed visit
- Start and stop dates of concomitant medications

Subjects who are alive at the time of data cut-off will be right censored on the date the subject was last known to be alive.

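### Two of the ten programmed safety queries in SAP Table 4-2 contradict their own labels: the pancreatic query names an intestinal disease, and a row that excludes polyps uses a query that includes them

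*SAP*

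**What the plan says.** Safety and tolerability is the primary objective (Protocol 1.5.1.1), and AEPIs are analysed under Primary Endpoints in SAP 4.3.8. SAP 4.3.8.3 says that AEPIs "will be derived programmatically based on Sponsor-defined list of preferred terms", in line with a Safety Signal Detection Plan that is not among the documents. Table 4-2 then lists ten AEPIs, each with its MedDRA definition. Four rows matter here.

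- **Pancreatic adverse events:** two high-level terms (HLTs). The first is the acute and chronic pancreatitis term. The second is "HLT: pancreatitis disorders necrotizing entecorolitis (NEC". The SAP list of abbreviations expands NEC as "Necrotizing Entecorolitis".
- **Benign neoplasia:** the label is "Benign neoplasia of the Gastrointestinal tract including the hepatobiliary system (not including polyps". Two standardised queries (SMQs) define it, one for gastrointestinal premalignant disorders and one named "SMQ: Biliary neoplasms benign (incl cysts and polyps) (Level 3, narrow terms".
- **Liver transaminase increase:** defined by "SMQ Drug related hepatic disorders - comprehensive search (broad and narrow terms".
- **Neoplastic growth:** the label is "Acceleration of neoplastic growth including Intestinal neoplastic growth/hypertrophic effect including polyps", and the definition is the whole neoplasm System Organ Class (SOC).

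AEPIs are tabulated by SOC and Preferred Term (PT) and by dose level, with further tables for relatedness, grade, seriousness, action taken with the study drug, and death.

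**The concern.** When a flag is set by program, a wrong definition carries straight through to the output. In the pancreatic and benign neoplasia rows the label promises one set of events and the definition selects another. A reader of the AEPI output would take the label at face value, and a programmer would have to choose between following the text and quietly correcting it.

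The pancreas matters because the protocol treats it as a named risk: gallbladder, biliary and pancreatic disease is an AE of special interest (AESI), monitored through lipase and amylase (Protocol 6.2.2). Apart from the infection and sepsis list in Table 4-4, Table 4-2 is the only programmed event list in the SAP. It therefore serves as the check on investigator classification of pancreatic events.

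**Working it through.** No arithmetic applies. The check compares each label with its definition and then asks what literal programming would do.

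**Pancreatic row**
1. The label concerns the pancreas; the second term names a bowel disease.
2. The abbreviation list gives the same expansion with the same misspelling. This is therefore the SAP's own text and not damage from reading the PDF.
3. There are three possible outcomes. (a) The string matches no HLT, so the row reduces to acute and chronic pancreatitis, and any other pancreatic disorder the second term was meant to catch is not flagged. (b) The programmer reads it as enterocolitis, and bowel events are flagged as pancreatic in a trial of lower gastrointestinal disease. (c) The programmer substitutes the term presumed to be intended, and the output departs from the signed SAP. None of these is what the label and the text together specify.
4. The documents do not say which term was intended. It has to be looked up in MedDRA 24.0, the version named in SAP 4.3.8.1.

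**Benign neoplasia row**
1. The label excludes polyps without qualification and covers the hepatobiliary system.
2. The second query includes polyps by name, and no exclusion step is given.
3. Biliary polyps captured by that query would therefore be flagged in a row that says it omits them. The conflict lies in one of the row's two queries and concerns biliary terms only.

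**Transaminase row**
1. The label names one laboratory finding. The definition is a comprehensive hepatic search with broad and narrow terms.
2. By name alone the search is wider than the label. The documents do not list its contents, so the excess cannot be itemised.

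**Neoplasm row**
1. The label is general. Intestinal growth and polyps are introduced as inclusions, not as the limit of the row.
2. It follows the class risk described in Protocol 1.8.1, which covers neoplastic growth in general as well as colon polyps. The whole SOC is consistent with that label.
3. Underlying diseases include leukaemias (SAP 4.3.5), and SAP 4.3.9.11 states: "Hematologic malignancy relapse/progression will be identified by manual review of reported malignancies or relapses in the AE data". Treatment-emergent relapses coded to this SOC would share the row with new or intestinal neoplasms. That is a lack of separation, not a contradiction.

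**The case against.** The best defence is that little depends on these rows.

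- AEPIs are descriptive, and neither the other endpoints nor the Toxicity Guidance Rule (Protocol 6.6.3) is built on them.
- Pancreatitis is still caught by the first HLT. Amylase and lipase have CTCAE shift tables (SAP 4.3.8.4), and all treatment-emergent events are tabulated by SOC and PT (SAP 4.3.8.1.2).
- AESIs, including pancreatic disease, colorectal polyps and newly diagnosed malignancies, come from the eCRF (SAP 4.3.8.2) and do not use Table 4-2.
- A misplaced enterocolitis or biliary polyp would still appear under its own PT.
- The unseen Safety Signal Detection Plan may hold the correct terms.

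All of this limits the harm. It does not make the two definitions usable as written. AESI status rests on what the site recorded, so the programmed list is the independent check, and that check should select what it claims to select.

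Three stronger readings are tempting, and the documents do not support them. First, a reader might infer that the neoplasm row is also mislabelled, that it counts every relapse, and that relapses would hide an intestinal signal. The label is general. AEPIs are treatment-emergent, a window that closes 28 days after the last dose (SAP 4.3.8.1), while follow-up runs to two years. The PT display keeps different events on separate lines. The SOC to which a relapse codes depends on a dictionary that the documents do not reproduce. Second, one might say that liver GVHD or bilirubin events will be reported as transaminase rises. That depends on SMQ contents that are not in the documents, and ALT and AST rises are reported directly from laboratory data in SAP 4.3.8.4. Third, one might conclude that pancreatic events have in fact been missed or invented. The program is not available, so only the written specification can be faulted.

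**Conclusion.** The point holds for two of the ten rows. The pancreatic definition contains an intestinal disease, and the benign neoplasia row uses a query whose name contradicts its exclusion of polyps. Both conflicts are visible in the SAP's own words and need no outside source. The consequence is a wrong or unpredictable set of events under those two labels in the treatment-emergent AEPI output, at both the primary and the end-of-trial analyses if the table is reused. The number of subjects affected cannot be estimated from the documents. The SAP also does not say whether a count per AEPI row will be shown; if the tables show only SOC and PT, the error affects which events enter them.

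The transaminase row is a lesser labelling point, because its search is named more broadly than its label. Separating relapse within the neoplasm row would be a presentational improvement and does not correct an error.

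The conclusion assumes that Table 4-2 was, or will be, programmed as written. The correction should be made, because these are the sponsor's own safety categories under the primary objective and it costs little.

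**What to change.** 1. Replace the second pancreatic term with the exact intended HLT, verified in MedDRA 24.0, and correct the NEC entry in the list of abbreviations.
2. Make the benign neoplasia row consistent: either remove polyp terms from the biliary query, or drop the exclusion from the label.
3. Rename the transaminase row to match its hepatic search.
4. Optionally, within the neoplasm row, flag treatment-emergent relapse or progression of the underlying malignancy, using the list finalised under SAP 4.3.9.11, and show the remaining neoplasms separately.
5. Re-run the AEPI flags and note the correction in the SAP or the trial report. If the earlier program already used the intended terms, say so.

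The cost is an edit to one table and one abbreviation entry, a dictionary look-up and a re-run. No new data are needed.
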